3.3 Prognosis of patients with FLL-HCC

Historically, FLL-HCC has been perceived as the more indolent counterpart of typical HCC, but patients with metastatic, unresectable disease face a grim prognosis. While patients with resected disease can do extremely well, with 5-year and median survival outcomes of up to 76% and 112 months, respectively, those with unresectable disease fare much worse, surviving only 12-14 months [11-13]. The presence of lymph node metastases has also been significantly associated with shorter recurrence-free and overall survival times [4,11]. Growing evidence suggests that patients with FLL-HCC appear to have a prognosis similar to that of patients with typical HCC without cirrhosis [4,21,22], suggesting that absence of cirrhosis and not an intrinsically less aggressive disease biology, may drive the natural history of FLL-HCC [4]. A pediatric series found no significant differences in 5-year event-free and overall survival between 36 typical HCC and 10 FLL-HCC patients of all stages who were randomized to two different cisplatin-based chemotherapy regimens following surgery or biopsy [21]. Approximately 80% of all patients had advanced and/or unresectable disease, and survival was uniformly poor regardless of histologic subtype (13.6 months for FLL-HCC vs. 3.3 months for typical HCC, $p = 0.16$). The estimated progression-free survival at 6 months in FLL-HCC and typical HCC patients were 50% and 30%, respectively [21]. Of note, these values were derived from a treatment-naïve patient population and it is anticipated that the PFS6 for a heavily pretreated FLL-HCC would be lower at approximately 40%.

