4.1 OVERVIEW OF STUDY DESIGN/INTERVENTION

4.2 Design

This is a multi-institutional randomized three arms phase II clinical trial, consisting of two parts. In Part 1 of this study, patients with advanced (recurrent or metastatic), unresectable FLL-HCC will be randomized to one of three arms: Arm A (everolimus 7.5 mg PO QD); Arm B (EDT with letrozole 2.5 mg PO QD + leuprolide 7.5 mg IM monthly); or Arm C (everolimus + EDT). Upon disease progression, patients in Arm A or Arm B may proceed to Part 2 of the study in which they will receive combination therapy with both everolimus and EDT. Please refer to Figure 1 (page 4) for a schematic of the study design.

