6.1 CRITERIA FOR SUBJECT ELIGIBILITY

6.2 Subject Inclusion Criteria

- Patients \geq 12 years old.

MEMORIAL SLOAN-KETTERING CANCER CENTER
IRB PROTOCOL

IRB#: 11-211 A(6)

- Pathologically confirmed diagnosis of advanced and/or unresectable FLL-HCC. This will be performed by the participating centers on submitted specimens. If the submitted material is insufficient for analysis, a repeat biopsy is recommended.
- ECOG performance status 0-2 (see Appendix 1); Lansky performance score of $\geq 60\%$ for patients 12-16 years old (see Appendix 2)
- Adequate hematologic, renal and hepatic function defined as:
 - Hematologic: ANC $\geq 1.0 \times 10^9/L$, platelets $\geq 50 \times 10^9/L$.
 - Renal: creatinine $\leq 2 \times$ upper limit of normal, or creatinine Clearance of $\geq 60 \text{ cc/mL}/1.73 \text{ m}^2$ for patients > 16 years old. For patients ≤ 16 years of age, creatinine Clearance of $\geq 70 \text{ cc/mL}/1.73 \text{ m}^2$ or serum creatinine based on the following chart:

Creatinine clearance or radioisotope GFR $\geq 70 \text{ ml/min}/1.73 \text{ m}^2$ or serum creatinine based on age/gender as follows:

Age	Maximum Serum Creatinine (mg/dL)	
	Male	Female
10 to < 13 years	1.2	1.2
13 to < 16 years	1.5	1.4
≥ 16 years	1.7	1.4

The threshold creatinine values in this Table were derived from the Schwartz formula for estimating GFR (Schwartz et al. J. Peds, 106:522, 1985) utilizing child length and stature data published by the CDC.

- Hepatic: total bilirubin $\leq 2 \text{ mg/dL}$, alanine and aminotransferase levels $\leq 5 \times$ upper limit of normal for age.
- Fasting blood glucose $< 1.5 \times$ upper limit of normal . If fasting glucose $\geq 1.5 \times$ upper limit of normal, adequate glycemic control (fasting glucose $< 1.5 \times$ upper limit of normal) for three weeks is recommended before starting protocol therapy.
- At least 1 target lesion measurable by Response Evaluation Criteria in Solid Tumors (RECIST 1.1) guidelines.
 - Target lesion(s) must not lie within a previously resected, irradiated, ablated, or chemoembolized area. If a lesion does lie in such an area, there must be evidence of a $\geq 20\%$ increase in diameter and/or the appearance of a new lesion on subsequent imaging in order for such a lesion to be considered a target lesion.
- Prior systemic therapy is allowed. Prior surgery, locoregional ablative or embolic therapies are also permitted provided that the criteria for measurable disease as outlined above are met.

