14.0 BIOSTATISTICS

Primary efficacy endpoints for Part 1 of protocol

- The primary efficacy endpoints for Part 1 of the study is progression-free survival at 6 months (PFS6).
- A progression event refers to the first evidence of radiographic disease progression, clinical progression as determined by study investigators, or death.
- Imaging performed in 6 months will be used to determine PFS6.
- PFS6 will be defined as the percentage of patients who are alive and have not experienced a progression event as defined above at 6 months from the date that study therapy was initiated. Patients that come off study before the 6 months scan will be considered events for the primary endpoint analysis.
- PFS6 will be assessed using a Simon's minimax two stage design, hypothesizing an improvement in PFS6 from 40% to 64% with the study regimen. Sixteen patients will be enrolled onto each of Arms A, B and C for a total of 48 patients in the first stage. Accrual will stop till the progression status at 6 months is obtained on all 16 patients in each arm. If 6 or less patients in one arm are progression free at 6 months the regimen in that arm will be terminated; otherwise, if 7 or more patients are alive and progression free at 6 months, enrollment will be extended in that arm to 28 patients (maximum total of 84 patients). At the end of stage 2, the respective regimens will be declared promising if 15 or more of the 28 patients in each arm are alive and progression free at 6 months. The design assumes a type I error (falsely accepting a non-promising therapy) and type II error (falsely rejecting a promising therapy) both set to 10%.

Figure 4: Simon's minimax 2 stage design (schematic applicable for each study arm)

- The probability of early termination due to drug inefficacy is 53%. In the event that 2 or more arms show promising activity, we will use the “pick the winner” format based on the randomized phase II clinical trials approach proposed by Simon et al. In this case, the regimen that has at least 15 patients progression free at 6 months and exceeds by at least 2 patients the number of progression free patients in the second best arm would be declared the winner. The probability of selecting the better regimen is 85%; the probability that no regimen is selected is 7%, while the probability of a tie is approximately 6% [149].

Secondary endpoints

- Secondary endpoints are:
 - Median PFS
 - Median overall survival (OS)

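### Does testing each arm against a 40% PFS6, a rate anticipated for heavily pretreated patients, undermine the decision rule when patients without prior systemic therapy may also enrol?

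*Combined protocol and SAP*

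**What the plan says.** Section 14.0 (primary efficacy endpoints for Part 1) assesses PFS6 separately in each arm with a minimax two-stage design, "hypothesizing an improvement in PFS6 from 40% to 64% with the study regimen". An arm continues if at least 7 of its first 16 patients are alive and progression-free at 6 months, and is called promising if at least 15 of 28 are. Both error rates are set at 10%, and the probability of early termination is given as 53%. Patients who leave the study before the 6-month scan count as events.

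The reference rate is explained in section 3.3. A paediatric series is quoted: "The estimated progression-free survival at 6 months in FLL-HCC and typical HCC patients were 50% and 30%, respectively". The section notes that these patients were treatment-naive and then says "it is anticipated that the PFS6 for a heavily pretreated FLL-HCC would be lower at approximately 40" per cent. That series included "10 FLL-HCC patients of all stages who were randomized to two different cisplatin-based chemotherapy regimens", and "Approximately 80% of all patients had advanced and/or unresectable disease" in it.

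Section 6.2 requires "Pathologically confirmed diagnosis of advanced and/or unresectable FLL-HCC" and adds "Prior systemic therapy is allowed"; prior surgery and locoregional treatment are also permitted. In section 4.2, patients with advanced, "unresectable FLL-HCC will be randomized to one of three arms", all of them experimental. Section 15.2 stratifies by site only.

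**The concern.** By the protocol's own account PFS6 depends on prior treatment. It takes the lower, pretreated figure as the bar for every arm, yet entry is not confined to pretreated patients. If many patients without prior systemic therapy enrol, and they would do better than 40% on an inactive regimen, the bar is too low: the 10% type I error is no longer a ceiling and an inactive arm stops early less often than 53% of the time.

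The randomisation does not help here, because it compares three experimental arms with one another and gives no estimate of the no-benefit rate. Section 14.0 shows operating characteristics only at 40% and 64% and does not plan PFS6 by prior therapy. A bare pass of 15 or 16 out of 28 could then reflect drug activity or case mix.

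**Working it through.** **Inputs from section 14.0.** n1 = 16, stop at 6 or fewer; n = 28, promising at 15 or more; null 40%, alternative 64%.

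**Formulas (exact binomial, one arm).**
- Early stopping: PET(p) = P(X1 ≤ 6), with X1 ~ Bin(16, p).
- Call promising: A(p) = Σ over x1 = 7 to 16 of P(X1 = x1) × P(X2 ≥ 15 − x1), with X2 ~ Bin(12, p).

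**Step 1: reproduce the stated design.** A(0.40) = 9.9%, PET(0.40) = 52.7% and A(0.64) = 90.2%. These agree with the stated 10%, 53% and 90% power. A search over two-stage designs found no smaller maximum than 28 that meets both error limits.

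**Step 2: the same rule at other no-benefit rates.**

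| True no-benefit PFS6 | Type I error | Early stopping |
|---|---|---|
| 35% | 3.2% | 68.8% |
| 40% | 9.9% | 52.7% |
| 42.5% | 15.5% | 44.5% |
| 45% | 22.8% | 36.6% |
| 50% | 41.5% | 22.7% |

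**Step 3: what a mixed population implies.** Let pretreated patients have 40%, and let a share f without prior systemic therapy have rate u. Then p = 0.40 + (u − 0.40)f. Only the 40% and 50% come from the documents; f and the other values of u are assumptions.

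| u | Type I error, f = 25% | Type I error, f = 50% |
|---|---|---|
| 30% | 5.9% | 3.2% |
| 35% | 7.7% | 5.9% |
| 45% | 12.5% | 15.5% |
| 50% | 15.5% | 22.8% |

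The sign turns on whether u lies above or below 40%. The protocol's only figure for u is 50%, from 10 patients. If that were 5 of 10 (the protocol gives an estimate, not a count), the exact 95% interval would be 19% to 81%, which covers every row.

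**Step 4: the off-study rule.** Suppose a fraction L of would-be successes leave before the 6-month scan for reasons other than progression and are counted as events. The observed rate is then p(1 − L). L is an assumption.

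| L | Type I error, p = 40% | p = 42.5% | p = 45% | Power at 64% |
|---|---|---|---|---|
| 5% | 6.6% | 10.6% | 16.2% | 82.6% |
| 10% | 4.1% | 6.9% | 10.9% | 72.4% |

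The loss that brings the observed rate back to 40% is L = 1 − 0.40/p. It is 5.9% for a true rate of 42.5% and 11.1% for 45%.

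**Step 5: could PFS6 by prior therapy settle it?** Take a bare pass of 15/28, split for illustration as 4/7 without and 11/21 with prior systemic therapy. The exact 95% intervals are 18% to 90% and 30% to 74%. They overlap almost entirely, so the split can neither show nor exclude a case-mix effect.

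**The case for a change.** The strongest case for a change is that the rule is sensitive to a rate the protocol itself says varies with prior therapy. On the protocol's own 40% and 50%, a quarter of patients without prior therapy would move the false-positive risk per arm from about 1 in 10 to about 1 in 6. The off-study rule offsets this only if the losses happen to be the right size, and it costs power. Prior treatment records are already sent at registration (section 15.1.1), so a table of error rates and a descriptive PFS6 by prior therapy would cost little.

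The sensitivity is real and the arithmetic stands. The step to a defect does not, for three reasons.

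- **The 50% does not carry over to this trial.** It describes 10 patients of all stages given cisplatin-based chemotherapy after surgery or biopsy. The figure of about 80% advanced or unresectable covers the whole series, not those 10. This trial enrols only advanced or unresectable disease, so the no-benefit rate in its patients without prior systemic therapy could be 40% or lower.
- **No prior systemic therapy is not the same as treatment-naive.** Section 6.2 admits patients after surgery and locoregional treatment, and section 3.4 describes repeated resections before systemic therapy is used. Such patients may have been treated extensively without any systemic drug.
- **The additions would not change a decision.** A table of error rates restates a property of every design with a fixed null. The subgroup results would be too imprecise to interpret a bare pass. Section 14.0 already plans objective response with exact 95% intervals, which is a more direct sign of activity.

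**Conclusion.** No change is needed. Section 14.0's figures are correct for the null it names, and section 3.3 says where that null comes from and which patients it describes; not repeating this in section 14.0 is only a missing cross-reference. Type I error per arm would run from 3.2% at a true no-benefit rate of 35% to 22.8% at 45%. The documents do not say where in that range, or beyond it, the enrolled mix lies. The share without prior systemic therapy is unknown, their no-benefit rate is unknown, and the off-study rule pushes observed PFS6 down by an unknown amount.

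A fixed historical rate in an uncontrolled phase II screen is a fair trade-off in a disease this rare. A reader who wants the error rates at another null can compute them from the stated cut-offs, and the analysts can describe prior treatment from records already collected. The conclusion would differ if the documents showed that most patients would be without prior systemic therapy and that their no-benefit PFS6 exceeds 40%. They show neither.

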Follow-up after study therapy

Patients who have discontinued the study will be asked to return four weeks later for an exit visit consisting of a medical history, vital signs, physical examination, toxicity check and blood tests including a complete blood count, Na, K, Cl, HCO₃, BUN, creatinine, glucose, AST, ALT, INR/PT/PTT, Ca, Mg, phosphorus, alkaline phosphatase, LDH, fasting blood glucose, fasting lipid panel, and ammonia. Patients who were on EDT will also be asked to provide blood to test serum estrogens, testosterone and FSH. After this exit visit, patients may be contacted every 3 months to monitor their survival. This information may also be checked through medical records or updated mortality lists of the institutions. Patients will also be encouraged to continue with periodic imaging after they have completed the study.

Correlative studies

Correlative studies are particularly important for rare diseases like FLL-HCC, and can be used to enhance the quantity and quality of information obtained from this study. Serum and tissue biomarker studies will be correlated with study outcomes to determine if they may have any predictive or prognostic value. Changes in biomarker expression in post-treatment specimens will also provide information about the precision of therapeutic targeting.

All specimens, including those procured at UCSF, JHU and DF/BWCC/MGHCC will be shipped to MSKCC or Labcorp and will be analyzed where the sample is sent.

- **Tissue biomarker analysis**

Tissue procurement and processing

- During screening, a block(s) of archived formalin-fixed paraffin-embedded FLL-HCC tumor tissue will be collected prior to the study and will be sent to the central laboratory facility at MSKCC along with the corresponding pathology report. Alternatively, approximately 20 unstained slides (if available) will be sent.
- Adequate samples should be sent to the pathology core lab facility at MSKCC, preferably within 4 weeks of beginning the study to permit adequate time to evaluate the samples and determine if additional samples are required.

MEMORIAL SLOAN-KETTERING CANCER CENTER IRB PROTOCOL

IRB#: 11-211 A(6)

- **For MSKCC patients:** samples are to be sent to the attention of [name], Department of Pathology, [name].
- **For participating sites:** samples are to be sent to the attention of Study 11-211, [name], [name].

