 - Objective response rate by RECIST 1.1 guidelines
 - Rate of conversion to resectable status
 - Safety and toxicity
 - Correlative serum and tissue biomarker studies.
- Kaplan-Meier PFS will be measured from the date that study therapy is initiated until the date of

first evidence of radiographic disease progression, global clinical deterioration as determined by study investigators, or death.

- Kaplan-Meier OS will be measured from the date that study therapy was commenced until the date of death.
- Objective responses will be reported using RECIST guidelines (version 1.1). Objective response will be estimated using binomial proportions and exact 95% CIs will be provided.
- Conversion to resectable status to be determined by hepatobiliary surgeons in conjunction with radiological assessment of response to therapy.
- Adverse events/toxicity will be monitored and recorded using the CTCAE version 4.0 and summarized descriptively.
- Baseline serum measurements will be correlated with PFS6 (binary endpoint) using Fisher's exact test for categorical serum measurements and using Wilcoxon rank sum test for continuous measurements. For each time point at which serum measurements are collected, changes in the different binary serum markers from baseline will be correlated with PFS6 using conditional logistic regression to account for the paired nature of the data while Wilcoxon signed-rank test will be used for continuous measurements.
- Associations between baseline tissue biomarkers and PFS6 will be assessed using Fisher's exact test for categorical biomarkers, trend tests for ordinal biomarkers and Wilcoxon rank-sum test for continuous biomarkers. For patients undergoing surgery, changes in tissue biomarkers from baseline to surgery will be summarized descriptively in an exploratory fashion.

Exploratory analysis for Part 2 of protocol (combination therapy).

- PFS will be evaluated for patients who were on Arm A (everolimus) or Arm B (EDT) during Part 1 of the study who subsequently received combined everolimus + EDT during Part 2.
- PFS will be measured as the time from the start of the combination therapy till progression or death whichever comes first.

Biomarker analysis and data interpretation

- Baseline tissue biomarkers will be correlated with PFS6.
- Baseline levels of hormones will be correlated with PFS6.
- Baseline levels of tumor markers will be correlated with PFS6.

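### Baseline markers are tested only against yes/no PFS6, so progressions after month 6 are ignored; using Part 1 PFS time would recover roughly 20 points of power at the cost of wording

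*Combined protocol and SAP*

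**What the plan says.** Section 14.0 (Secondary endpoints) sets the serum analysis: "Baseline serum measurements will be correlated with PFS6 (binary endpoint) using" Fisher's exact test for categorical measurements and a Wilcoxon rank-sum test for continuous ones. Tissue markers follow the same pattern: "Associations between baseline tissue biomarkers and PFS6 will be assessed using Fisher's exact test for categorical biomarkers", with trend tests for ordinal and rank-sum tests for continuous markers. The closing list on biomarker analysis repeats the choice for each class: "Baseline tissue biomarkers will be correlated with PFS6", "Baseline levels of hormones will be correlated with PFS6" and "Baseline levels of tumor markers will be correlated with PFS6". Section 14.0 contains no log-rank or Cox analysis of any marker.

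The same section defines a time-to-event version of the outcome in the same patients: "Kaplan-Meier PFS will be measured from the date that study therapy is initiated until the date of" first progression, clinical deterioration or death.

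Section 10.0 (Correlative studies) describes the aim more broadly: "Serum and tissue biomarker studies will be correlated with study outcomes to determine if they may have any predictive or prognostic value". It names no test for this. It mentions PFS6 for the baseline stains and no other outcome.

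No alpha, power, effect size, marker prevalence or sample size is given for the marker tests.

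**The concern.** PFS6 gives one yes/no value per patient. A patient who progresses at month 7 and one still progression-free at month 30 are recorded alike. In a trial that accrues over several years, many progressions fall after month 6, and the marker tests use none of them.

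Section 10.0 presents the correlative work as especially valuable because the disease is rare. Sample size cannot realistically be raised, so the efficiency of the analysis is one of the few things still open to choice. At stake is the chance of missing a real marker association that the data already being collected could show.

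**Working it through.** **1. The plan's own figures.** Section 14.0 gives a Simon minimax design per arm: PFS6 40% v 64%, stop at 6 or fewer of 16, promising at 15 or more of 28. Exact binomial calculation gives type I error 0.099, power 0.902 and early termination 0.527. The stated 10%, 10% and 53% reproduce. There is no stated figure for the marker tests to reproduce.

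**2. Information kept by six-month status.** With exponential PFS and S = PFS6, the information on the log hazard ratio per patient, near no effect, is:
- six-month status: S(ln S)²/(1−S)
- PFS time followed to month f: the event probability, 1−S^(f/6)

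At S = 0.50 the first is 0.50 × 0.4805/0.50 = 0.480. At f = 12 the second is 1−0.25 = 0.75, so the ratio is 64%.

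| PFS6 | Status information | kept v 6 mo | v 12 mo | v 24 mo | v complete |
|---|---|---|---|---|---|
| 40% | 0.560 | 93% | 67% | 57% | 56% |
| 50% | 0.480 | 96% | 64% | 51% | 48% |
| 64% | 0.354 | 98% | 60% | 43% | 35% |

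The loss is 33-40% at 12 months. At 24 months it is 43-49% for PFS6 of 40-50%, and 57% for PFS6 of 64%. The 6-month column shows that the order of events before month 6 is worth only 2-7%. Nearly all of the loss is progressions after month 6.

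**3. Closed-form power check.** Assumptions not in the documents: two-sided 5%, hazard ratio 2, even marker split, arms pooled. Take N = 84 and overall PFS6 50%.
- Six-month PFS in the two marker groups solves (s + s²)/2 = 0.5, giving s = 0.618 and s² = 0.382.
- Fisher's exact test, 42 v 42: power 54%.
- Events by 12 months: 42(1−0.618²) + 42(1−0.382²) ≈ 62.
- Log-rank power (Schoenfeld): Φ(√62 × ½ × ln 2 − 1.96) = Φ(0.77) = 78%. At 24 months (about 77 events) it is 86%.
- With PFS6 40% throughout: 59% v 82-88%. With 64% throughout: 39% v 68-82%.

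**4. Calendar and follow-up.** Section 7.0 gives 2 patients a month, and Section 14.0 halts accrual after 48 patients until six-month status is known. Accrual is then 48/2 + 6 + 36/2 = 48 months. If analysis follows 6 months after the last entry (assumed), first-stage patients have about 54−12 = 42 months of potential follow-up on average and second-stage patients 54−39 = 15. The mean is (48×42 + 36×15)/84 ≈ 30 months.

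**5. Simulated power on that calendar.** Hazard ratio 2, 50% prevalence, assessments every 12 weeks, true PFS6 64/40/40, 1,500 trials per scenario. Ranges are across independent runs.

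| Analysis | Power, all 84 patients |
|---|---|
| Fisher on PFS6 (as planned) | 52-55% |
| PFS6 status, stratified by arm | 57-58% |
| PFS time, unstratified log-rank | 74% |
| PFS time, stratified by arm | 78-80% |

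Like for like, the gap is 74−53 = 21 points unstratified (Fisher gave 53% in that run) and about 79−58 = 21 stratified. Moving from Fisher to a stratified test on PFS6 accounts for about 5 points.

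**6. With the stage 1 stopping rule.** An arm continues with probability 0.473 at 40% and 0.972 at 64%. All three continue with probability 0.473² × 0.972 = 0.22. Expected N is 48 + 12(2×0.473 + 0.972) = 71. Power is then about 41% (Fisher) v 68-72% (stratified PFS time).

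**The case against.** The strongest reply is that these are secondary correlative analyses with no stated power, that relating markers to the primary endpoint is coherent, and that the broader wording in Section 10.0 does not exclude PFS time as a further outcome. All of that stands. No stated figure is wrong, and this is an efficiency point.

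A second reply concerns the data. Section 14.0 counts patients who leave before the six-month scan as events, but only for the primary endpoint, and gives no rule for Kaplan-Meier PFS. After removal, Section 13.0 requires survival monitoring only, and Section 10.0 merely encourages further imaging. Progression times after withdrawal may therefore be missing, and censoring there may be informative. This stands too, and the fix must deal with it. It does not remove the gain: with all 84 patients and an assumed 3% a month non-informative dropout, counted as events for PFS6 and censored for PFS time, power is 42% v 71%.

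Third, the inputs could be less favorable. The background section on the PI3K/Akt/mTOR pathway reports overexpression of mTOR in about 25% of tumors. At 25% prevalence with the stopping rule, power is 33% v 59%. Both figures fall and the gap remains.

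A reader might also infer that the plan treats an early progression and one just before month 6 alike at material cost. The calculation does not support that: PFS time cut at month 6 gave 57% power against 58% for stratified six-month status.

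**Conclusion.** The point holds as an efficiency weakness. Relating every baseline marker to PFS6 alone loses roughly one third to one half of the information, somewhat more if PFS6 is near 64% and follow-up is long. Like for like, that is about 20 points of power in the 64/40/40 scenario.

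A reader might infer that the trial would have about 80% power with PFS time and that the yes/no endpoint alone brings it down to about 55%. The documents do not support that. The pair needs all 84 patients, which is a ceiling reached about 22% of the time at 64/40/40 and 11% if every arm is at 40%. It also needs an alpha, hazard ratio and prevalence that the plan does not give, and part of the gap comes from stratification and Fisher's conservatism. With the stopping rule applied, about 41% v 68-72% is the fairer pair.

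The conclusion rests on proportional hazards and on follow-up well past month 6. If a marker's effect fades after month 6, or the PFS cutoff is early, the gain shrinks.

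**What to change.** In Section 14.0, make the main analysis of each baseline tissue and serum marker a Cox model (or a log-rank or score trend test) of Part 1 PFS time, stratified by randomized arm. Keep the planned PFS6 tests as supportive description.

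Add two statements:
- How patients who leave before progression are handled. For example, censor at the last adequate tumor assessment, with a sensitivity analysis that counts them as events as PFS6 does. Kaplan-Meier PFS needs such a rule in any case.
- The data cutoff for PFS, since the gain depends on follow-up past month 6.

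The cost is wording: no further patients, visits or assays. The downsides are a proportional-hazards assumption, tied event times from scheduled scans (which standard software handles), and possibly informative censoring after withdrawal, which the sensitivity analysis addresses. The change should be made before outcome data are examined, so that it is not a post hoc switch of endpoint.
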